1.1. Synopsis

Protocol Title: A Phase 1, Randomized, Placebo-Controlled Study to Evaluate the Tolerability, Safety, Pharmacokinetics, and Immunogenicity of LY3832479 Given as a Single Intravenous Dose in Healthy Participants

Short Title: A Phase 1, Randomized, Placebo-Controlled Study to Evaluate LY3832479 in Healthy Participants

Rationale:

Lilly is developing LY3832479 for the treatment and prevention of coronavirus disease 2019 (COVID-19). Study J2Z-MC-PGAA (PGAA) will investigate the safety, tolerability, and pharmacokinetics of LY3832479 when administered as a single intravenous dose to healthy participants.

Objectives and Endpoints

Objectives	Endpoints
Primary	

To investigate the safety and tolerability of a single dose of LY3832479 in healthy participants	
Serious and nonserious adverse events, laboratory measures of safety, ECG, and vital signs
Secondary	
AUC, Cmax

Abbreviations: AUC = area under the concentration versus time curve; Cmax = maximum observed drug concentration; ECG = electrocardiogram; IV = intravenous.

Overall Design

Study PGAA is a Phase 1, randomized, placebo-controlled study of LY3832479 administered to healthy participants.

The study will comprise up to 3 cohorts, each with an intended number of participants as follows:

Cohorts 1 and 2

At least 9 participants:

- 7 randomized to LY3832479 and
- 2 randomized to placebo.

Cohort 3

At least 8 participants:

- 6 randomized to LY3832479 and
- 2 randomized to placebo.

Participants will be initially monitored for safety within the study site where they will be admitted on Day -1, dosed on Day 1, discharged on Day 4, and subsequently monitored on an outpatient basis until the last follow-up visit.

[figure not shown]
Disclosure Statement: This is a sequential, single-ascending dose study with up to 3 cohorts that is participant and investigator blinded.

Number of Participants:

A maximum of 30 participants will be enrolled to study intervention such that approximately 8 participants have sufficient evaluable data in each of the 3 cohorts.

Intervention Groups and Duration:

Single-dose study with an estimated duration for each participant of up to 16 weeks from screening through follow-up.

Data Monitoring Committee: No**1.2. Schema**

Abbreviations: LY = LY3832479; PBO = placebo; PK = pharmacokinetics.

Note: After at least 7 participants have completed Day 4 in a given cohort, all safety data up to this cutoff date will be reviewed to determine whether the next cohort can be enrolled after agreement between Lilly's medical monitor and the investigator.

Figure 1. Single-ascending dose schema for Study J2Z-MC-PGAA.

1.3. Schedule of Activities (SoA)

Procedure / Assessments	Screening	Dosing					Postdose Follow-up Visits							Comment
Visit Number	V1	V2				V3	V4	V5	V6	V7	V8	V9	V10/ED	
Week(s)		0				1	2	3	4	6	8	10	12	
Study Day	-14 to -2	-1	1	2	3	4	8 ±1d	15 ±2d	22 ±2d	29 ±3d	43 ±3d	57 ±3d	71 ±3d	85 ±3d
Informed consent (written)	X													
Review/confirm inclusion/exclusion criteria	X	X	Predose											
Medical history including pre-existing conditions	X													
Weight/height	X												X	
Urinalysis	X													
COVID-19 clinical screening	X	X					X	X	X	X	X	X	X	
SARS-CoV-2 serology		X					X		X		X		X	

Procedure / Assessments	Screening	Dosing					Postdose Follow-up Visits							Comment
Visit Number	V1	V2				V3	V4	V5	V6	V7	V8	V9	V10/ED	
Week(s)		0				1	2	3	4	6	8	10	12	
Study Day	-14 to -2	-1	1	2	3	4	8 ±1d	15 ±2d	22 ±2d	29 ±3d	43 ±3d	57 ±3d	71 ±3d	85 ±3d
Nasal or nasopharyngeal swab		X												
Admission to study site/check in (admission day may vary depending on IP availability)		X												
SARS-CoV-2 point-of-care test		X												
Discharge from study site						X								

Procedure / Assessments	Screening	Dosing					Postdose Follow-up Visits								Comment
Visit Number	V1	V2				V3	V4	V5	V6	V7	V8	V9	V10/ED		
Week(s)		0				1	2	3	4	6	8	10	12		
Study Day	-14 to -2	-1	1	2	3	4	8 ±1d	15 ±2d	22 ±2d	29 ±3d	43 ±3d	57 ±3d	71 ±3d	85 ±3d	
Physical examination (PE)/Medical assessment (MA)	X	X	Predose			X	As needed								X
Vital signs: blood pressure, pulse rate ^a	X	X	Predose, every 15 min during infusion; every 30 min until 2h after end of infusion; then every 60 min until 6h after end of infusion.	24 h (±2 h)	48 h (±2 h)	X	X	X	X	X	X	X	X	X	Vital signs should be taken following an at least 5-min rest in a supine position. Vital signs may be taken any time prior to dosing.
Body temperature	X	X	Predose, 6 h (±15 min)	24 h (±2 h)											May be performed at additional time points at the discretion of the investigator.
Single 12-lead ECG ^a	X		Predose, 1 h (±10 min), 6 h (±15 min)	24 h (±2 h)	48 h (±2 h)		X	X		X			X		All ECGs are local. Predose ECG can be taken any time prior to dosing on same day.

Procedure / Assessments	Screening	Dosing					Postdose Follow-up Visits							Comment
		V1	V2				V3	V4	V5	V6	V7	V8	V9	V10/ED
Visit Number	V1	0				1	2	3	4	6	8	10	12	
Study Day	-14 to -2	-1	1	2	3	4	8 ±1d	15 ±2d	22 ±2d	29 ±3d	43 ±3d	57 ±3d	71 ±3d	85 ±3d
Concomitant medications and AE review	X	X	Predose	X	X	X	X	X	X	X	X	X	X	AE only after participant has signed the study informed consent form.
HIV, hepatitis B/C serology	X													
Pregnancy test (women only) ^b	X	X												Serum pregnancy test at screening. Day -1 urine test refers to test at check-in; this is not needed if check-in occurs on same day as screening. Postdose urine test(s) can be performed at the judgment of the investigator, if pregnancy is suspected.
Clinical laboratory tests ^a	X		Predose		X		X	X	X	X	X	X	X	Fasting is not required for these tests.

Procedure / Assessments	Screening	Dosing					Postdose Follow-up Visits							Comment	
		V1	V2				V3	V4	V5	V6	V7	V8	V9	V10/ED	
Visit Number	V1	0				1	2	3	4	6	8	10	12		
Week(s)															
Study Day	-14 to -2	-1	1	2	3	4	8 ±1d	15 ±2d	22 ±2d	29 ±3d	43 ±3d	57 ±3d	71 ±3d	85 ±3d	
Breath or urine ethanol screen		X													Ethanol test is on the day of check-in. If screening visit is the same as day of check-in, no further ethanol test is required. Ethanol screen may be repeated at other time points at the discretion of the investigator.
Urine drug screen		X	X												Day -1 urine test refers to test at check-in; this is not needed if check-in occurs on same day as screening. Drug screen may be repeated at other time points at the discretion of the investigator.
IV LY3832479 or placebo dosing				X											Participants will be randomized to receive either LY3832479 or placebo. Dosing may be delayed due to IP being unavailable; see Section 4.1.

Procedure / Assessments	Screening	Dosing					Postdose Follow-up Visits							Comment	
Visit Number	V1	V2				V3	V4	V5	V6	V7	V8	V9	V10/ED		
Week(s)		0				1	2	3	4	6	8	10	12		
Study Day	-14 to -2	-1	1	2	3	4	8 ±1d	15 ±2d	22 ±2d	29 ±3d	43 ±3d	57 ±3d	71 ±3d	85 ±3d	
LY3832479 PK sampling ^a		Predose, end of infusion (±10 mins), 6 hours (±30 mins) after start of infusion.	24 h (±2 h)	48 (±2 h)		X	X		X	X	X			X	
Immunogenicity sample ^a		Predose					X		X		X		X		
Serum sample for exploratory biomarkers ^a		X		X			X		X		X		X		
Pharmacogenetics sample ^a		Predose													For storage only.

Abbreviations: AE = adverse event; COVID-19 = coronavirus disease 2019; ECG = electrocardiogram; ED = early discontinuation; HIV = human immunodeficiency virus; I/E = inclusion/exclusion criteria; IV = intravenous; PK = pharmacokinetics; SARS-CoV-2 = severe acute respiratory syndrome coronavirus 2; V = Visit

- a When conducted on the same day, the order of procedures should be vital signs, ECG, and then blood sampling.
- b For women who are considered to be postmenopausal, follicle-stimulating hormone should be drawn to confirm postmenopausal status if necessary, according to Appendix 4 (Section 10.4).

2. Introduction

Given the current epidemiologic emergency caused by the coronavirus disease 2019 (COVID-19) pandemic, Eli Lilly and Company (Lilly) is seeking opportunities to identify potential prophylactic and treatment options to help in the prevention and control of this public health issue. Recently, Lilly entered into a co-development agreement with TopAlliance Biosciences, Inc. to develop LY3832479 (also known as JS016-CB6, JS016, or CB6). LY3832479 is a recombinant, fully human neutralizing monoclonal immunoglobulin (Ig) G1 kappa antibody with abrogated Fc effector function.

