6.1. Study Interventions Administered

Intervention Name	LY3832479	Placebo
Type	Biologic	Not applicable
Dose Formulation	Solution for infusion	0.9% sodium chloride solution
Unit Dose Strength(s)	400-mg vial	Placebo
Dosage Level(s)	
 • Cohort 1: 700 mg • Cohort 2: 2800 mg • Cohort 3: 7000 mg 	Not applicable
Route of Administration	IV infusion	IV infusion
Use	Experimental	Placebo
IMP and NIMP	IMP	IMP
Sourcing	Provided by Lilly	Provided by site
Packaging and Labeling	Provided in glass vials and labeled appropriately	Per site procedure

Abbreviations: IMP = investigational medicinal product; IV = intravenous; NIMP = noninvestigational medicinal product.

This following table describes the infusion volume and rate for LY3832479. Placebo volume and rate will match the LY3832479 dose cohort.

The infusion rate may be reduced as deemed necessary if an infusion reaction is observed. To ensure close monitoring, participants will remain in or close to their bed for at least 6 hours after completion of the infusion.

LY3832479 Dose (mg)	Volume withdraw from DP vial (mL)	Volume of sterile diluent (mL)	Total infusion volume (mL)	Start infusion rate(duration)
700	17.5	32.5	50	100 mL/h (30 min, allowable range 25 - 60 min)
2800	70	None	70	100 mL/h (42 min, allowable range 37 – 75 min)
7000	175	None	175	100 mL/h (105 min, allowable range 100 - 150 min)

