8.5. Pharmacokinetics

Venous blood samples will be collected as specified in the SoA for determination of serum concentrations of LY3832479 used to evaluate the PK for LY3832479.

A maximum of 5 samples may be collected at additional time points during the study if warranted and agreed upon between the investigator and the sponsor.

Instructions for the collection and handling of biological samples will be provided by Lilly.

Site personnel will record

- the date and time (24-hour clock time) of administration (start and end of infusion), and
- the date and time (24-hour clock time) of each PK sample.

It is essential that the times are recorded accurately.

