9.3.1 Pharmacokinetic analysis

Any PK analyses prior to database lock will be the responsibility of Eli Lilly PK/PD group, whereas any PK analyses post database lock will be reported by Covance.

Noncompartmental methods applied with a validated software program (Phoenix WinNonlin Version 8.1 or later) to the serum concentrations of LY3832479 will be used to determine the following PK parameters, when possible:

Parameter	Units ^a	Definition
AUC(0-t _{last})	µg.h/mL	Area under the concentration versus time curve from time zero to time t, where t is the last time point with a measurable concentration
AUC(0-∞)	µg.h/mL	Area under the concentration versus time curve from time zero to infinity
%AUC(t _{last} -∞)	%	Percentage of AUC(0-∞) extrapolated
C _{max}	µg/mL	Maximum observed drug concentration
t _{last}	h	Time of the last observed drug concentration
t _{max}	h	Time of maximum observed drug concentration
t _½	h	Half-life associated with the terminal rate constant (λ_z) in non-compartmental analysis
CL	L/h	Total body clearance of drug calculated
V _z	L	Volume of distribution during the terminal phase
V _{ss}	L	Volume of distribution at steady state

^aSerum LY3832479 drug concentration units will come in from the bioanalytical lab as ng/mL to one decimal place; the data will be transformed to µg/mL for analysis.

Additional PK parameters may be calculated, as appropriate.

The software and version used for the final analyses will be specified in the CSR. Any exceptions or special handling of data will be clearly documented within the final study report.

Formatting of tables, figures and abbreviations will follow the Eli Lilly Global PK/PD/TS Tool: NON-COMPARTMENTAL PHARMACOKINETIC STYLE GUIDE. The version of the tool effective at the time of PK analysis will be followed.

General PK Parameter Rules

- Actual sampling times will be used in the final analyses of individual PK parameters, except for non-bolus pre-dose sampling times which will be set to zero.
- C_{max} and time of maximum observed drug concentration (t_{max}) will be reported from observed values. If C_{max} occurs at more than one time point, t_{max} will be assigned to the first occurrence of C_{max} .

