- Also, where two or more consecutive concentrations are BQL towards the end of a profile, the profile will be deemed to have terminated and therefore any further quantifiable concentrations will be set to missing for the calculation of the PK parameters unless it is considered to be a true characteristic of the profile of the drug.

Individual Concentration vs. Time Profiles

- Individual concentrations will be plotted utilizing actual sampling times.
- The terminal point selections will be indicated on a semi-logarithmic plot.

Average Concentration vs. Time Profiles

- The average concentration profiles will be graphed using scheduled (nominal) sampling times.
- The average concentration profiles will be graphed using arithmetic average concentrations.
- The pre-dose average concentration for single-dose data from non-endogenous compounds will be set to zero. Otherwise, only quantifiable concentrations will be used to calculate average concentrations.
- Concentrations at a sampling time exceeding the sampling time window specified in the protocol, or $\pm 10\%$, will be excluded from the average concentration profiles.
- Concentrations excluded from the mean calculation will be documented in the final study report.

- A concentration average will be plotted for a given sampling time only if 2/3 of the individual data at the time point have quantifiable measurements that are within the sampling time window specified in the protocol or $\pm 10\%$. An average concentration estimated with less than 2/3 but more than 3 data points may be displayed on the mean concentration plot if determined to be appropriate and will be documented within the final study report.

Treatment of Outliers during Pharmacokinetic Analysis

Application of this procedure to all PK analyses is not a requirement. Rather, this procedure provides justification for exclusion of data when scientifically appropriate. This procedure describes the methodology for identifying an individual value as an outlier for potential exclusion, but does not require that the value be excluded from analysis. The following methodology will not be used to exclude complete profiles from analysis.

Data within an Individual Profile

A value within an individual profile may be excluded from analysis if any of the following criteria are met:

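### The end-of-infusion PK window permits a draw while the infusion is still running, which can only lower observed Cmax; the loss is modest because the 6 h sample caps it

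*Protocol*

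**What the plan says.** Protocol 1.3 (Schedule of Activities) sets the Day 1 PK samples at "Predose, end of infusion (±10 mins), 6 hours (±30 mins) after start of infusion". The window around the end of infusion is symmetric, and the next sample is timed from the start of infusion.

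Protocol 6.1 gives the starting rate and duration for each dose:
- 700 mg: "100 mL/h (30 min, allowable range 25 - 60 min"
- 2800 mg: "100 mL/h (42 min, allowable range 37 – 75 min"
- 7000 mg: "100 mL/h (105 min, allowable range 100 - 150 min"

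SAP 9.3.1 states that Cmax and tmax "will be reported from observed values". It also says "Actual sampling times will be used in the final analyses of individual PK parameters", apart from the pre-dose time. Under Protocol 8.5, sites record the date and clock time "of administration (start and end of infusion), and" those of every PK sample.

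The only timing exclusion in SAP 9.3.1 begins "Concentrations at a sampling time exceeding the sampling time window specified in the protocol, or". It goes on to a ±10% tolerance and removes values from the average concentration profiles only.

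Cmax is a secondary endpoint (Protocol 3; SAP 4.2). It also enters the dose-proportionality power model, which compares the highest with the lowest dose (SAP 9.3.2).

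**The concern.** With an intravenous infusion, serum concentration rises until the infusion stops, so the true peak is at that moment. A window that is symmetric in time is not symmetric in effect. A few minutes late costs almost nothing with a long half-life, whereas a few minutes early means that part of the dose has not yet been given. Actual sampling times put the value at the right place on the time axis and protect AUC, but they cannot recover a peak that was not sampled.

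The fixed 10 minutes is also a larger share of a 30-minute infusion than of a 105-minute one, so the error could differ between the two doses whose ratio is used to judge dose proportionality. With 6 or 7 active participants per cohort, a few early draws could move a cohort geometric mean. No rule in SAP 9.3.1 addresses a sample that is inside the window but taken during the infusion.

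**Working it through.** **1. Planned durations.** Volume divided by rate (Protocol 6.1): 50/100 h = 30 min, 70/100 h = 42 min, 175/100 h = 105 min. All three match the protocol.

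**2. Dose delivered 10 minutes before the end**, (T − 10)/T:

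| Dose | Planned duration | Shortest allowed duration |
|---|---|---|
| 700 mg | 20/30 = 66.7% | 15/25 = 60.0% |
| 2800 mg | 32/42 = 76.2% | 27/37 = 73.0% |
| 7000 mg | 95/105 = 90.5% | 90/100 = 90.0% |

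These figures bound the early sample. They are not the error in reported Cmax, because that is the larger of the early sample and the 6 h sample.

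**3. Model for reported Cmax.** From Table 4.1 at 700 mg:
- CL = 700 mg / 75 mg·h/mL = 9.33 mL/h
- V1 = 700 mg / 0.253 mg/mL = 2767 mL

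The documents give no distribution parameters. I assumed Q 10-60 mL/h and V2 2-3 L. The resulting terminal half-life is about 15-23 days, inside the 2 to 4 weeks projected in Protocol 4.3.

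With k10 = CL/V1, k12 = Q/V1 and k21 = Q/V2, let α and β be the roots of x² − (k10 + k12 + k21)x + k10·k21 = 0, with weights A = (α − k21)/(α − β) and B = (k21 − β)/(α − β). For an infusion of length T:
- during infusion, C(t) ∝ (A/α)(1 − e^(−αt)) + (B/β)(1 − e^(−βt))
- after infusion, each term is its value at T times e^(−α(t−T)) or e^(−β(t−T))

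Reported fraction = max[C(T − 10 min), C(6 h)] / C(T).

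| Reported Cmax as % of true | 700 mg | 7000 mg |
|---|---|---|
| Every draw 10 min early, Q 10-60 | 88-96% | about 91-97% |
| Draws spread evenly over ±10 min, Q 10-60 | about 95-98% | about 97.5-99% |
| Every draw 10 min late, Q 10-60 | at least 99.6% | at least 99.6% |
| Every draw 10 min early, Q 120 | about 80% | about 91% |

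At 700 mg, with the draw at the early limit, the 6 h value is the observed maximum in every one of these cases. tmax then moves from about 0.5 h to about 6 h.

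**4. Dose-proportionality scale.** The doses differ 10-fold, so the shift in power-model slope is log10 of the bias in the 7000/700 dose-normalized ratio. For Q 10-60 it is about +0.004 to +0.014 if every draw is at the early limit, and about +0.002 to +0.012 if draws are spread evenly.

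**5. Wider sensitivity.** A second parameterization fixes Cmax at 0.253 and AUC at 75 from Table 4.1, sets the terminal half-life at 14 or 28 days, and varies an assumed distribution half-life. Loss in reported Cmax at the early limit:

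| Distribution half-life | 700 mg | 7000 mg |
|---|---|---|
| None (one compartment) | 0.6-1.1% | 0.4-0.9% |
| 24-72 h | 3.1-10.7% | 2.4-8.4% |
| 12 h | 11.6-19.3% | 9.0-9.2% |
| 3-6 h | 19.0-32.8% | 8.4-9.2% |

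Across this grid, with every draw at the early limit, the 7000/700 ratio is inflated by 0.2% to 36% (slope +0.001 to +0.13). The upper end needs the fastest distribution.

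**6. AUC.** The whole area to 6 h is at most about 6 × 0.253 = 1.5 mg·h/mL, or 2.0% of the predicted 75. An error of one third in that part is about 0.7% of AUC(0-∞).

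**The case against.** The early-limit figures assume that every sample is taken at the extreme of the window, and nothing in the documents suggests that sites would do so. The study is exploratory and unpowered (Protocol 9.1, 9.2), and SAP 9.3.2 sets no acceptance limit for proportionality, so a slope shift near 0.01 is unlikely to alter a conclusion. These points stand, and they keep this a minor matter.

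Partial safeguards exist:
- Early draws can be identified from the recorded times.
- SAP 9.3.1 lets a questionable value be evaluated with and without it.
- Protocol 8.5 allows up to five extra samples.
- A compartmental analysis, which could use actual times and infusion duration, is optional (Protocol 9.4.3).
- The sponsor's collection instructions, which are not in these documents, might ask for a post-infusion draw.

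None of these, as written, names a compliant on-infusion sample or tells the analyst what to do with it.

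Three stronger readings are tempting. The first is that Cmax at 700 mg is understated by a third. That is the shortfall in the early sample, and the 6 h sample normally replaces it. The second is that the error falls mainly on the lowest dose. Under the base assumptions the gap between doses is about 1-3 percentage points, and a clear gap needs faster distribution, which the documents neither state nor exclude. The third is that early samples should be dropped as a source of Cmax. Removing one candidate from a maximum can never raise it. At 7000 mg with Q 120 mL/h it would lower reported Cmax from about 91% to 84-85% of true.

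**Conclusion.** The point holds as a small, one-directional weakness in the sampling rule. Assay error aside, a compliant draw before the end of infusion can only understate Cmax and may displace tmax to about 6 h, and no SAP rule deals with it specifically. For assumed Q 10-60 mL/h and V2 2-3 L, the loss at the early limit is about 4-12% at 700 mg and 3-9% at 7000 mg. Averaged over an even spread of draw times it is about 2-5% and 1-2.5%. The size depends on how many samples are drawn early and on how fast the antibody distributes, and the documents give neither. AUC is barely affected, and the primary safety endpoints are not touched.

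**What to change.** In the Schedule of Activities, make the window one-sided: 0 to +10 minutes after the recorded end of infusion. In the models above, a late draw then costs at most about 2.6% even with the fastest distribution assumed, and nearly the same in each cohort.

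In SAP 9.3.1, flag any sample drawn before the recorded end of infusion. Report Cmax, tmax and the Cmax dose-proportionality result with and without the participants concerned. Do not delete the early sample and let the 6 h value stand as Cmax. The SAP part remains useful if sampling is already complete, because the times it needs are recorded under Protocol 8.5.

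The cost is a slightly tighter window for site staff, a wording change in both documents and one added sensitivity summary. No extra blood sample is needed. The analysis without flagged participants will be less precise in cohorts of 6 or 7 active participants, so it should sit beside the main result and not replace it.

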2.1. Study Rationale

Lilly is developing LY3832479 for the treatment and prevention of COVID-19. Study J2Z-MC-PGAA (PGAA) will investigate the safety, tolerability, and pharmacokinetics (PK) of LY3832479 when administered as a single intravenous (IV) dose to healthy participants.

2.2. Background

The viral pathogen causing the COVID-19 pandemic is the severe acute respiratory syndrome coronavirus 2 (SARS-CoV-2). Viral entry into host cells involves its structural Spike glycoprotein. The Spike glycoprotein attaches itself via its receptor-binding domain (RBD) to the human angiotensin-converting enzyme 2 (ACE2), enabling sufficient proximity for the virus to fuse with the target cell membrane. ACE2 is expressed in the membrane of various cell types in a variety of tissues, primarily in the lung, small intestine, kidney, and vascular endothelium (Hamming et al. 2004; Human Protein Atlas Project website [WWW]).

LY3832479 specifically binds the Spike glycoprotein RBD with high affinity, preventing its interaction with the ACE2 human receptor. This in turn blocks viral cell fusion, preventing SARS-CoV-2 invasion of human cells, inhibiting viral replication. As the binding epitope of LY3832479 to RBD covers the most conserved RBD/ACE2 interaction site based on an analysis of the LY3832479-RBD complex x-ray structure, LY3832479 is expected to neutralize all currently described viral strains.

The amino acid sequence of recombinant antibody LY3832479 was derived from human memory B cells of a convalescent patient with COVID-19. Therefore, formation of antidrug antibodies (ADAs) and related side effects is unlikely. To further reduce potential toxicity to human cells, point mutations (L234A, L235A; LALA mutation) were introduced into the Fc domain of the native human IgG1 antibody to eliminate Fc effector function, to reduce the risk of antibody-dependent enhancement (ADE).

